ВМА	X	Time points for disease assessments described in notes At screening, suspected CR and then after 6 months, 12 months, and yearly (± 1 month) a achieving CR (provided CR is maintained clinically) until WOC, initiation of subseque anticancer therapy, participant lost to FU, des or defined EOS. Optional (investigator discreat suspected PD. If all criteria for CR are metexcept percent plasma cells in BM, then additional BMA should be performed every 3						months, 12 months, and yearly (± 1 month) after achieving CR (provided CR is maintained clinically) until WOC, initiation of subsequent anticancer therapy, participant lost to FU, death, or defined EOS. Optional (investigator discretion) at suspected PD. If all criteria for CR are met except percent plasma cells in BM, then additional BMA should be performed every 3 months until CR is achieved, as long as other CR criteria are maintained.		
BMA for cytogenetics (FISH/karyotyping)	Х	See Section 8.1.2							See Section 8.1.2	

Visit Identifier	Screening	Treatment Period (Each 28 Day Cycle)				EOT FU Visit LTFU Visit			Notes/Protocol Section	
		Day 1	Day 4	Day 8	Day 15	Day 22				Day 4 Visit is Cycle 1 only
Visit Window	Day -28 to Day -1	Cycles 2 and later ± 3D	-1/+3D	Cycle 1 -1/+3D Cycles 2 and later ± 3D	±3D	± 3D	≤14D post-final dose	28 to 35 days post-final dose	Q12W ± 14D	
BMB/BMA	X		Tin	ne points for	r disease	assessm	ents describ	ed in notes		At screening and to confirm sCR. Either BMA or BMB can be used; however, the same method should be used for a participant throughout the study. Optional (investigator discretion) at suspected PD. See Section 8.1.2
Contraception check	X	Х					X	Х	Х	Only required for WOCBP. Through 5 months post last dose of study intervention. See Section 5.3.1
Pregnancy test	X	X					X	Х		Only required in WOCBP. Also to be done whenever 1 menstrual cycle is missed during the active treatment period and up to 90 days post last dose of study intervention (or when potential pregnancy is otherwise suspected). Serum required at screening. See Section 8.2.7 and Table 8.
Hematology/chemistry	X	Х	Cycle1	Cycle 1	Cycle 1	Cycle 1	Х	Х		See Section 8.2.6 and Table 8. For Cycle 1 Day 4, hematology only.
Serum quantitative immunoglobulins (IgG, IgM, IgA, IgD, IgE)	Х	Х					Х	Х		See Section 8.2.6 and Table 8.
CMV testing (quantitative PCR)		X*								*Every 1 to 3 months depending on risk factors See Section 8.2.6, Table 8, and Appendix 14.
PT/INR	Х									See Section 8.2.6 and Table 8

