5.3. Lifestyle Considerations

5.3.1. Contraception

The investigator or his or her designee, in consultation with the participant, will confirm that the participant is utilizing an appropriate method of contraception for the individual participant from the permitted list of contraception methods (see Appendix 4 Section 10.4.4) and will confirm that the participant has been instructed in its consistent and correct use. At time points indicated in the SoA (including long term follow-up visit/contacts covering the required contraception period [through 5 months post last dose of study intervention for WOCBP [Appendix 4 Section 10.4]), the investigator or designee will inform the participant of the need to use highly effective contraception consistently and correctly and document the conversation and the participant's affirmation in the participant's chart (participants need to affirm their consistent and correct use of at least 1 of the selected methods of contraception). Contraception check is only required for WOCBP. In addition, the investigator or designee will instruct the participant to call immediately if the selected contraception method is discontinued and document the requirement to use an alternate protocol-specified method, including if the participant will no longer use abstinence as the selected contraception method, or if pregnancy is known or suspected in the participant. If a participant is confirmed to be pregnant, study intervention should be discontinued.

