8.2.7. Pregnancy Testing

A serum pregnancy test is required at screening; thereafter, pregnancy tests may be urine or serum tests, but must have a sensitivity of at least 25 mIU/mL. Pregnancy tests will be performed in WOCBP at the times listed in the SoA. Following a negative pregnancy test

result at screening, appropriate contraception must be commenced and a second negative pregnancy test result will be required at the baseline visit prior the participant's receiving the study intervention. Pregnancy tests will also be done whenever 1 menstrual cycle is missed during the active treatment period (or when potential pregnancy is otherwise suspected), at the end of treatment visit and at the follow-up visit. Pregnancy tests may also be repeated if requested by IRBs/ ECs or if required by local regulations. If a urine test cannot be confirmed as negative (eg, an ambiguous result), a serum pregnancy test is required. In such cases, the participant must be excluded if the serum pregnancy result is positive.

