10.4.2. Female Participant Reproductive Inclusion Criteria

A female participant is eligible to participate if she is not pregnant or breastfeeding, and at least 1 of the following conditions applies:

• Is not a WOCBP (see definitions below in Section 10.4.3).

OR

• Is a WOCBP and using a contraceptive method that is highly effective (with a failure rate of <1% per year), as described below, during the intervention period and for at least 5 months after the last dose of study intervention, which corresponds to the time needed to eliminate any reproductive safety risk of the study intervention(s). If a highly effective method that is user dependent is chosen, a second effective method of contraception, as described below, must also be used. The investigator should evaluate the effectiveness of the contraceptive method in relationship to the first dose of study intervention.

The investigator is responsible for review of medical history, menstrual history, and recent sexual activity to decrease the risk for inclusion of a woman with an early undetected pregnancy.

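### The Schedule of Activities ends the mandatory missed-cycle pregnancy test 90 days after the last dose, about 62 days before the protocol's own 5-month reproductive risk period ends

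*Protocol*

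**What the plan says.** All of the text below is in the Protocol and concerns women of childbearing potential (WOCBP).

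- **Section 1.3, pregnancy-test row.** Scheduled tests end at the follow-up visit, 28 to 35 days after the last dose, and the long-term follow-up column is empty. The note adds a rule for missed cycles: "Also to be done whenever 1 menstrual cycle is missed during the active treatment period and up to 90 days post last dose". The same note also calls for a test when pregnancy is suspected for another reason, and gives no end date for that.
- **Section 1.3, contraception-check row.** The check runs "Through 5 months post last dose of study intervention", and long-term follow-up is marked.
- **Section 5.3.1.** Contraception is covered "through 5 months post last dose of study intervention for WOCBP". The section also says that "the investigator or designee will instruct the participant to call immediately if the selected contraception method is discontinued", "or if pregnancy is known or suspected in the participant".
- **Section 10.4.2.** Highly effective contraception is required "for at least 5 months after the last dose of study intervention, which corresponds to the time needed to eliminate any reproductive safety risk".
- **Section 8.2.7.** "Pregnancy tests will be performed in WOCBP at the times listed in the SoA". The section then repeats the missed-cycle rule without any post-treatment extension: "Pregnancy tests will also be done whenever 1 menstrual cycle is missed during the active treatment period (or when potential pregnancy is otherwise suspected").

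**The concern.** The protocol names one period over which a pregnancy could be exposed to elranatamab, and it is 5 months. Section 4.2.3 explains why this matters: developmental toxicity has not been studied. Up to day 90 a missed cycle by itself obliges the site to test. From day 90 to month 5 the protocol still regards the risk as present, but a missed cycle leads to a test only if someone judges it suspicious. No reason is given for ending the obligation earlier than the contraception requirement. At stake is how soon a pregnancy in an already treated participant is recognised. Nothing in the efficacy or safety analysis depends on it.

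**Working it through.** The plan states no figure for this gap, so there is none to reproduce. The check is date arithmetic followed by a look at what still operates inside the gap.

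**Inputs**
- End of the missed-cycle rule: day 90 after the last dose (Protocol 1.3).
- End of the reproductive risk period: 5 months after the last dose (Protocol 10.4.2, 5.3.1, 1.3).
- Conversion: 30.4375 days per month and 365.25 days per year (SAP 5.2.12).
- Long-term follow-up: every 12 weeks ± 14 days (Protocol 1.3), or every 3 months from the last dose (Protocol 7.1).
- Contraceptive failure rate: below 1% per year (Protocol 10.4.2).
- Participants treated: 187 (Protocol 2.2.3.2).

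**Length of the gap**
- SAP conversion: 5 × 30.4375 = 152.2 days; 152.2 − 90 = 62.2 days; 62.2 / 152.2 = 41%.
- Shortest five calendar months: 28 + 31 + 30 + 31 + 30 = 150 days; gap 60 days; 60 / 150 = 40%.
- Longest five calendar months: 31 + 30 + 31 + 30 + 31 = 153 days; gap 63 days; 63 / 153 = 41%.
- If a menstrual cycle is taken as 28 days (an assumption), 62.2 / 28 = 2.2 cycles.

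**Scheduled contacts inside the gap**
- Counting by 12 weeks: first contact 84 ± 14 = days 70 to 98; second 168 ± 14 = days 154 to 182.
- Counting by 3 months with the same window: first 91 ± 14 = days 77 to 105; second 182 ± 14 = days 168 to 196.
- On either count no long-term follow-up contact is scheduled from day 106 to day 152. Participants who stopped treatment without confirmed progression are the exception, because Section 7.1 keeps their disease assessments going at least every 4 weeks.

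**Rough ceiling on pregnancies arising in the gap**
- Per adherent woman: below 1% × 62.2 / 365.25, or about 0.17%.
- If all 187 treated participants were WOCBP, which overstates the number: 187 × 0.0017 = about 0.32 expected pregnancies at most. The documents do not give the true number of WOCBP.

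**After the change** the missed-cycle rule would end at about day 152 (150 to 153), and the gap would be 0.

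**The case against.** The best defence is that contraception prevents exposure while testing detects it, so the two windows need not be equal. The 90 days also coincides with the minimum period of active adverse event collection after the last dose in Section 8.3.1. Testing through active safety collection, with contraception continuing longer, would be a coherent design. The match is real, but the protocol never offers it as the reason. Nor does it fit the reporting rule: Section 8.3.5.1 covers a pregnancy found after treatment has stopped and sets no 90-day limit.

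A second objection is that the change would detect very little. This largely stands. It adds no scheduled contact, so for most participants a missed cycle would surface only when the woman reports it. She is already told to call if pregnancy is suspected, and the site must already test on suspicion. What the change removes is the discretion over whether a missed cycle counts as suspicion. The main protection, effective contraception through 5 months, is unaffected. The participant is also already off drug, so a positive test would not alter dosing.

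Three stronger readings are tempting, and the documents do not support them.

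- **That pregnancies after day 90 go untested or unreported.** Testing on suspicion and exposure reporting both continue without a stated end.
- **That Section 8.2.7 contradicts the Schedule of Activities by stopping at the end of treatment.** It refers to the Schedule for test times and forbids nothing, so its shorter wording is incomplete rather than conflicting.
- **That the 90 days is an oversight left from an earlier contraception period.** The amendment history does show a 90-day contraception period set in Amendment 5 and revised requirements in Amendment 10. But Amendment 10 lists Section 1.3 among the sections changed, so keeping 90 days there could equally have been deliberate. The point rests on the current text alone.

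**Conclusion.** The mismatch is real and internal to the protocol. The mandatory missed-cycle test ends about 62 days (60 to 63) before the period that Section 10.4.2 ties to reproductive risk, and no reason is stated. The length of the gap depends only on how a month is counted.

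The safety consequence is small: recognition of a rare pregnancy could come somewhat later than it need. The ceiling of about 0.32 pregnancies assumes adherence to contraception and deliberately overcounts the women at risk. Enrollment closed in January 2022, so a change now reaches only WOCBP still on treatment or within 5 months of their last dose. The 41% describes the length of the wording gap. It should not be read as a loss of detection. No endpoint, sample size or statistical analysis is affected. This is a cheap improvement.

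**What to change.** In the pregnancy-test note of the Schedule of Activities, replace 90 days with 5 months. Put the same missed-cycle wording in Section 8.2.7 so that the two agree.

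Home testing need not be added. The home urine test in Appendix 8 is a measure for public emergencies, and making it routine would be a new procedure that this alignment does not require.

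The cost is two wording edits and an occasional extra urine test, which Table 8 already makes the standard method after screening. Section 10.1.1 requires ethics approval for design amendments and health authority approval for substantial ones, so the edit should travel with the next protocol amendment and does not justify one of its own.

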2. INTRODUCTION

Elranatamab (PF-06863135), a novel BsAb that targets both BCMA on MM cells and CD3 on T-cells, is currently being developed for the treatment of RRMM.

2.1. Study Rationale

The purpose of the study is to evaluate whether single-agent elranatamab can provide clinical benefit in participants with RRMM who are refractory to at least one PI, one IMiD and one anti-CD38 mAb. Because it is unknown how prior treatment with BCMA-directed therapy will affect the activity of elranatamab, this study will enroll one cohort with participants who have not previously received BCMA-directed therapy (Cohort A) and one cohort with participants who have received previous treatment with BCMA-directed therapy (Cohort B).

2.2. Background

2.2.1. Multiple Myeloma

MM is a hematological B-cell malignancy characterized by dysregulated proliferation of BM plasma cells. Globally, there are approximately 160,000 new cases and 106,000 deaths per year attributed to MM (Bray et al, 2018). The American Cancer Society estimates that for the US in 2020, approximately 32,270 new MM cases will be diagnosed and approximately 12,830 MM-related deaths will occur (Siegel et al, 2020).

Despite recent advances in treatment, MM remains an incurable disease and almost all patients, even those who initially respond to treatment, are expected to relapse. Even for patients who receive ASCT, the median time to relapse is only 17.2 months (Jimenez-Zepeda et al, 2015). Similarly, for patients who are treated with novel PI-based or IMiD-based combination regimens as frontline treatment, the median time to relapse is 16.4 months (Lopez et al, 2015).

Moreover, MM patients typically cycle through many lines of treatment, having become relapsed/refractory to various therapeutic approaches. Trials that have treated patients with BCMA-directed therapy in the RRMM population have included heavily pretreated patients; for example, 57% of patients studied by Trudel et al had received \geq 5 lines of therapy (Trudel et al, 2019) and other trials have included populations receiving a median of 6 (range 3-18) prior therapies (Mailankody et al, 2020) and a median of 5 (range 3 to 18) prior therapies (Berdeja et al, 2020b).

Outcomes in the RRMM population are quite poor; for example, patients with RRMM who respond poorly to PI-based or IMiD-based regimens show a median OS of only 1.5 years (Kumar et al, 2004). Newer and more effective therapies have substantially increased patient benefit; however, in this real-world setting (N=3449), the most recent 4-year survival is only 75% (Nandakumar et al, 2019). Results from 2 trials in patient populations similar to the current protocol are summarized in Table 1. The lack of effective and durable therapeutic options highlights the unmet medical need in the RRMM patient population.

Therapy	Prior therapy (eligibility)	Median number of prior therapies	ORR	DOR (months)	Reference
Belantamab mafodotin	IMiD, PI, anti-CD38	7	31% ^a 97.5% CI (20.8, 42.6)	6.3ª IQR (3.7, 7.7)	(Lonial et al, 2020b)
			34% ^b 97.5% CI (23.9, 46.0)	6.9 ^b IQR (4.8, 7.9)	
Selinexor + Dexamethasone	IMiD, PI, anti-CD38	7	26% 95% CI (19, 35)	4.4 95% CI (3.7, 10.8)	(Chari et al, 2019)

 Table 1.
 Efficacy Results from Trials in Similar Patient Population

a. Data from 2.5 mg/kg Q3W (the approved dosing regimen for belantamab mafodotin) cohort

b. Data from 3.4 mg/kg Q3W cohort

NOTE: For both studies, ORR and DOR were assessed by an independent review committee.

2.2.2. BCMA and CD3

BCMA is a transmembrane glycoprotein belonging to the TNFr SF 17 superfamily. BCMA is normally expressed exclusively in lymphocytes of the B-cell lineage, including plasmablasts and differentiated plasma cells, where it is involved in the regulation of B-cell maturation. BCMA is widely expressed on malignant plasma cells collected from patients with MM whereas BCMA is detected in a very small proportion of normal BM mononuclear cells from healthy volunteers (Sanchez et al, 2012b). Cleavage of cell surface BCMA by γ -secretase releases sBCMA (Laurent et al, 2015) which can act as a decoy for BCMA-directed antibodies. Inhibition of γ -secretase can reduce levels of sBCMA and increase activity of BCMA-directed therapies (Pont et al, 2019). sBCMA levels in serum are elevated in patients with MM and correlate with the proportion of MM cells in the BM microenvironment. sBCMA levels are independent of renal function, which permits its use as a biomarker in patients with renal insufficiency, and BCMA is detectable in the serum of patients with non-secretory disease (Ghermezi et al, 2017b). Moreover, patients in 2 studies with high baseline levels of sBCMA appeared to have poorer clinical outcomes (Sanchez et al, 2012a; Ghermezi et al, 2017a).

T-cells are potent immune cells capable of mediating adaptive immunity through the expression of antigen receptor complexes (TCR), which comprise an antigen-specific alpha-beta heterodimer and a transmembrane CD3 protein and mediate receptor signaling and T-cell activation (Smith-Garvin et al, 2009). TCRs recognize specific protein fragments (ie, peptides) presented by MHC proteins on APCs, virally infected cells, and tumor cells. Triggering of CD3 signaling in a CD8+ T-cell synapsed with another cell presenting a target antigen can cause the T-cell to release perforin and granzyme B, resulting in cancer cell lysis and death. Cancer cells can avoid T-cell recognition and destruction by down-modulating peptide/MHC presentation. One way to remove dependence on peptide/MHC presentation is through direct bridging of a cell-surface antigen on a target cell with the extracellular CD3 on T-cells, leading to T-cell signaling equivalent to that generated by MHC/TCR-based engagement.

2.2.3. Elranatamab (PF-06863135)

Elranatamab is a heterodimeric humanized full-length bispecific IgG2 kappa mAb against BCMA and CD3. Targeted T-cell-mediated cytotoxicity follows the binding of one epitope of elranatamab to CD3-expressing T-cells and a second epitope to BCMA-expressing MM cells.

2.2.3.1. Nonclinical Studies of Elranatamab

In vitro, elranatamab has been shown to induce cytokine release by human T-cells and to redirect patient T-cells to lyse tumor cells from MM patients in a concentration-dependent manner. Elranatamab also showed robust anti-tumor activity in vivo following a single dose in three different orthotopic human MM models established in immunodeficient mice engrafted with human T-cells, and greater potency was correlated with higher BCMA expression levels. In another orthotopic tumor model with low BCMA expression levels, a second dosing of elranatamab was found to delay tumor progression. As part of a secondary pharmacology assessment, elranatamab induced cytokine release in human whole blood, which was expected due to the presence of BCMA-expressing target cells, confirming the mechanism of action. Finally, two 1-month GLP toxicology studies in cynomolgus monkeys showed mechanism-based effects, including increased T-cell activation, increased cytokines and microscopic findings in the secondary lymphoid tissues. Decreases in circulating lymphocytes and serum globulins were also noted.

2.2.3.2. Clinical Overview

As of January 2023, elranatamab is being evaluated for the treatment of adult patients with RRMM or newly diagnosed MM in 11 ongoing studies. For detailed information on these studies, refer to the IB.

Enrollment in the current study (C1071003) completed in January 2022 with a total of 187 participants enrolled and treated. Study results on the safety, efficacy, clinical pharmacology and immunogenicity of elranatamab are provided in the IB.

2.3. Benefit/Risk Assessment

More detailed information about the known and expected benefits and risks and reasonably expected AEs of elranatamab may be found in the Investigator's Brochure, which is the SRSD for this study.

2.3.1. Risk Assessment

Potential Risk of Clinical Significance	Summary of Data/Rationale for Risk	Mitigation Strategy									
	Study Intervention: Elranatamab										
CRS	A known toxicity of therapeutics that function by activation of immune effector cells. Circulating cytokines are elevated after IV or SC administration of elranatamab. CRS signs and symptoms are expected mainly after the first and second dose and occasionally after the third dose or later of elranatamab. For further information, refer to the IB.	 Participants will be hospitalized for at least 2 days after the C1D1 dose and 1 day for the C1D4 dose for safety surveillance. Hospitalization from C1D1 to C1D5 may be considered. (see Section 6.1.1). The priming regimen is expected to mitigate rate, duration, and severity of CRS (see Section 4.3). Guidance for monitoring, grading, and management of CRS per ASTCT criteria and guidelines is included in Appendix 11. Dose modification/discontinuation in the setting of Grade ≥2 AEs (including CRS) is described in Section 6.6.2. This study will include only participants who are likely to tolerate potential events of CRS by excluding participants who are particularly susceptible to complications of CRS, including those with impaired cardiac function or clinically significant CV disease (see Section 5.1 and Section 5.2). Premedication (see Section 6.5.1). Additional management for Grade ≥3 CRS is described in Section 9.5.2. 									
ICANS	A known toxicity of therapeutics that function by activation of immune effector cells. Data from ongoing studies suggest ICANS is infrequent. For further information, refer to the IB.	Participants will be hospitalized for at least 2 days after the C1D1 dose and 1 day for the C1D4 dose for safety surveillance. Hospitalization from C1D1 to C1D5 may be considered. (see Section 6.1.1). The priming regimen is expected to mitigate the rate, duration, and severity of ICANS.(see Section 4.3). Regular neurologic examination will be performed by the investigator or designee (Section 8.2.2). Guidance for monitoring, grading, and management of ICANS per ASTCT criteria and guidelines is included in Appendix 11. Dose modification/discontinuation in the setting of Grade ≥2 AEs (including ICANS) is described in Section 6.6.2.									

Potential Risk of Clinical Significance	Summary of Data/Rationale for Risk	Mitigation Strategy					
	Study Interventio	n: Elranatamab					
		Additional management for Grade \geq 3 ICANS is described in Section 9.5.2					
Peripheral neuropathy including GBS	A common complication of multiple myeloma and its treatment. Grade 3 peripheral neuropathy has been observed with elranatamab.	This study excludes participants who may be particularly susceptible to new or worsening peripheral neuropathy, including those with POEMS syndrome, history of GBS or GBS variants, ongoing Grade ≥ 2 peripheral neuropathy, and history of prior neuropathy with BCMA-directed drugs (see Section 5.2).					
	For further information, refer to the IB.	Regular neurologic examinations will be performed by the investigator (or designee) to monitor for emerging signs and symptoms of new or worsening peripheral neuropathy.					
		The administration of drugs known to cause peripheral neuropathy should be carefully considered, and if possible, avoided by the investigator; effective treatment and prophylaxis for infections should be prioritized. (Section 6.5).					
		Participants should be closely monitored for signs and symptoms of neuropathy following infections or following the administration of any vaccine (Section 8.3.11).					
		Dose modification/discontinuation for peripheral neuropathy is described in Section $6.6.2$.					
		Work-up recommendations for new or worsening peripheral neuropathy (Grade ≥ 2) is described in Section 8.3.11.					
		Additional management for peripheral neuropathy is described in Section 9.5.2.					
Infections	Infections are common in patients with RRMM due to underlying immunosuppression. As elranatamab causes plasma cell depletion, and likely contributes to worsening hypogammaglobulinemia and neutropenia, elranatamab treatment increases the risk of infections. For further information refer to the IB.	See Section 6.5 and Appendix 14 for infection prophylaxis. Monitor participants, especially those with neutropenia, for signs of infection. See Section 6.6.2 for dose modifications for elranatamab.					

